## 3      **Investigational plan**

### 3.1      **Study design**

[figure not shown]
This is a multi-center, randomized, double-blind, double-dummy, parallel-group study evaluating the efficacy, safety and tolerability of 3 doses of LIK066 *vs* placebo and *vs* empagliflozin.

**Pre-Screening:** Pre-screening for some blood tests is possible (it is optional) and can be used to identify appropriate patients to be screened for this clinical study. The pre-screening visit includes blood tests for NT-proBNP, HbA1c, eGFR and serum potassium, which will be analyzed at the central laboratory. At Visit 1, these laboratory parameters will be assessed by the central laboratory, independently whether or not pre-screening was done for the patient.

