### Figure 3-1 Study design

#### 3.1.2 Epoch 2 (placebo run-in)

Patients meeting the eligibility criteria defined in [Section 4](#) will enter the placebo run-in (Epoch 2). During the approximately 2 weeks duration of Epoch 2, patients will receive single-blind placebo run-in medication as described in [Section 5.2](#).

At Visit 101, the patients' volume status must be assessed based on physical examination and laboratory values and, if hypovolemic, corrected during the run-in.

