**Table 6-1 Assessment schedule**

Epoch		1	2		3					4		
Visit	Pre-screen	1 Screen	101 Run-in	199 TD/ PPD	201 RND/ BL	202	203	204	299 TD A / PPD	301	302	399 TD A / PPD/ EOS
Week		-4	-2	0	2	4	8	12	24	36		
Screening assessments												
Pre-screening informed consent	S P											
Study informed consent		X										
Inclusion/exclusion (Section 4)		X		X*	X*							
Patient demographics (Section 6.2)		X										
Medical history		X										
Medical history: protocol solicited & Heart Failure/Diabetes		X										
Smoking & alcohol history (Section 6.2)		X										
Efficacy												
Height (Section 6.4.1)		X										
Weight / BMI (Section 6.4.1)		X C	X		X	X	X	X	X	X	X	X
Blood pressure (Section 6.4.8)		X	X		X	X	X	X	X	X	X	X
NYHA classification (see Section 6.4.4)		X	X		X	X	X	X	X	X	X	X
Body composition: bio-impedance (see Section 6.4.3)					X				X	X		X
Echocardiography (see Section 6.4.5)			X							X D		X D
NT-ProBNP (Section 6.4.2)	S P	X			X		X B		X B	X B		X B

Epoch		1	2	3					4			
Visit	Pre-screen	1 Screen	101 Run-in	199 TD/ PPD	201 RND/ BL	202	203	204	299 TD A / PPD	301	302	399 TD A / PPD/ EOS
Week		-4	-2	0	2	4	8	12	24	36		
Epoch 3 phase disposition								X				
Study completion												X
Sub-studies (subset of patients)												
Sub-study 1: DXA ( Section 6.4.3 & Section 6.5.5 ): Body composition/BMD					X					X D		X D
Sub-study 2: 24h urine collection ( Section 6.4.10 ) Bone biomarkers ( Section 6.5.3.4 ) Renal biomarkers ( Section 6.5.3.4 )					X				X G	X G		X G

RND = Randomization visit;

EOS = End of Study;

TD = study treatment discontinuation;

PPD = premature patient discontinuation;

X = assessment to be recorded on clinical data base;

S = assessment to be recorded on source documentation only;

\* = reassessed prior to randomization;

A = patients only discontinuing study medication need to have such assessments done per unplanned assessment eCRF;

B = laboratory values will be blinded;

C = BMI will be calculated at Visit 1;

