D = no echocardiography/DXA assessment for patients <12 weeks after Visit 201 with PPD/TD. If week 12 echocardiography/DXA done before PPD/TD, no repeat echocardiography/DXA needed for patients < 24 weeks after Visit 201;

G = urinary glucose values will be blinded;

T = only triglycerides

P = pre-screening for NT-proBNP, HbA1c, eGFR and serum potassium is optional (the pre-screening data will be handled as source documentation only). These laboratory parameters will be assessed from all patients by the central laboratory at Visit 1, independently whether or not pre-screening was done. At Visit 1, SAEs are to be collected from pre-screened patients only if the SAE is reported to be causally related with study procedures (i.e. blood sampling).

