### 6.4.2 NT-proBNP

NT-proBNP will be measured from a blood sample at visits indicated in [Table 6-1](#) and analyzed at a central laboratory. NT-proBNP measured at Visit 1 will be used for assessing an inclusion criterion (see [Section 4.1](#)) and will not be masked. The results of all NT-proBNP measurements after randomization (V201) will remain masked until final database lock, except that they will be extracted to a restricted area for the statistical/programming team to perform the analysis for the Week 12 analysis.

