## 9.8 Sample size calculation

The study planned to randomize approximately 496 patients in total, allocated in the ratio of 1:1:2:2:2 to the LIK066 2.5mg qd, 10mg qd, 50mg qd, empagliflozin and placebo treatment groups, respectively.

The following power calculations are based on the primary efficacy variable of log-transformed ratio of NT-proBNP at Week 12 to baseline. Due to the lack of available data in this patient population there is uncertainty on the standard deviation (SD) of the log-transformed ratio of week 12 to BL in NT-proBNP. Therefore calculations are provided for assumptions of SD in the range of 0.8, 0.85 to 0.9 to reflect the impact of this uncertainty on the power estimation. Based on the data from the PARAMOUNT HF study (data on file), a SD of 0.85 was considered a reasonable estimate.

Assuming a one-sided 2.5% significance level (with adjustments for multiple comparisons using the MCP-MOD), a sample size of approximately 496 patients (124 each in placebo and LIK high dose; 62 each in LIK low doses; 124 in empagliflozin that is not included in the dose-response modeling) will provide a mean power (over all candidate models) of 75%(or 90%) to detect a dose response signal, assuming that the underlying true maximum NT-proBNP reduction on LIK066 vs placebo is 25% (or 30%), and the standard deviation (on the log scale) is 0.85.

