2.1.1 General definitions

Study treatment, study medication or study drug

In this document, “study treatment”, “study medication” or “study drug” refers to the investigational, control drug or placebo of this study. Run-in study treatment, study medication or study drug refers to placebo matching LIK066/placebo matching Empagliflozin assigned to the patients during placebo run-in; double-blind study treatment, study medication or study drug refers to LIK066 2.5mg qd, LIK066 10mg qd, LIK066 50mg qd, Empagliflozin (up-titrated from 10mg qd to 25mg qd after 2 weeks) or placebo matching LIK066/placebo matching Empagliflozin assigned to a patient at randomization.

Run-in period

Run-in period refers to Epoch 2 (placebo run-in).

Double-blind period

Double-blind period refers to Epoch 3 (treatment period 1) + Epoch 4 (treatment period 2).

Baseline and study day

Baseline is defined as the last measurement obtained before or at the randomization visit. The first day of administration of randomized study treatment (first dose) is defined as Day 1 for the study. If the date of first administration is missing, then randomization date will be used as Day 1.

All other study days will be labeled relative to Day 1. For event dates on or after Day 1, study day for a particular event date is calculated as [Date of event] – [Date of first dose] + 1. For the dates before Day 1, study day for an event date is calculated as [Date of event] – [Date of first dose]. Duration of an event will be calculated as [Event end date] – [Event start date] + 1. The descriptor “Day 0” will not be used.

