2.5.2 Statistical hypothesis, model, and method of analysis

The Multiple Comparison Procedure-Modeling (MCP-MOD) method ([Pinheiro et al, 2006](#) & [Pinheiro et al, 2014](#)) as described in the study protocol will not be performed for the primary endpoint. The following analysis will be performed instead as an exploratory analysis for NT-proBNP. Statistical testing of hypotheses on the endpoint will be performed at the two-sided 0.05 significance level.

The change from baseline in log-transformed NT-proBNP at Week 12 will be analyzed using a mixed effect model of repeated measures (MMRM) in which LVEF at baseline (< 45% vs. \geq 45%), treatment group, visit, and treatment group-by-visit interaction will be included as fixed-effect factors, and baseline log-transformed NT-proBNP will be included as a covariate, with a common unstructured covariance matrix for all treatment groups. The analysis will be performed based on change from baseline in log-transformed NT-proBNP at all post-baseline scheduled visits up to Week 12 and based on likelihood method with an assumption of missing at random (MAR) for missing data. Based on the MMRM model, the estimates and the 95% confidence intervals will be provided for the adjusted means of the change from baseline in log-transformed NT-proBNP at Week 4 and at Week 12 for each treatment group, and for the adjusted mean difference at Week 4 and at Week 12.

The treatment effect (mean difference) of LIK066 doses vs. Placebo or LIK066 doses vs. empagliflozin will be analyzed using the MMRM model as described above including all treatment groups: LIK066 2.5mg qd, LIK066 10gm qd, LIK066 50mg qd, Empagliflozin 25mg qd and Placebo qd. For the comparison of LIK066 doses vs. Placebo, the treatment effects of LIK066 2.5mg qd vs. Placebo qd, LIK066 10mg qd vs. Placebo qd, and LIK066 50mg qd vs. Placebo qd will be presented; For the comparison of LIK066 doses vs. EMPA, the treatment effects of LIK066 2.5mg qd vs. Empagliflozin 25mg qd, LIK066 10gm qd vs. Empagliflozin 25mg qd, and LIK066 50mg qd vs. Empagliflozin 25mg qd will be presented. The analysis results will be back-transformed for ease of data interpretation.

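### The exploratory NT-proBNP model leaves out the Visit 1 value; adding it cannot bias the comparison and may narrow the Week 12 intervals by 0% to about 12%

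*SAP*

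**What the plan says.** SAP 2.5.2 replaces MCP-Mod with an exploratory MMRM for change in log NT-proBNP up to Week 12. The model contains LVEF group, treatment, visit and treatment-by-visit, and "baseline log-transformed NT-proBNP will be included as a covariate". The baseline covariate has no visit interaction. SAP 2.1.1 fixes which value this is: "Baseline is defined as the last measurement obtained before or at the randomization visit". SAP 2.5.3 imputes no missing NT-proBNP value.

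A second pre-randomization value is collected. A footnote to Protocol Table 6-1 says of NT-proBNP and the other pre-screening parameters: "These laboratory parameters will be assessed from all patients by the central laboratory at Visit 1, independently whether or not pre-screening was done". The table marks NT-proBNP with an X at Visit 1 (week -4) and at Visit 201 (week 0), and its legend reads "X = assessment to be recorded on clinical data base". The optional pre-screening value, by contrast, stays in source documents only. Protocol 6.4.2 gives the Visit 1 value one purpose: "NT-proBNP measured at Visit 1 will be used for assessing an inclusion criterion". The threshold in Protocol 4.1 is above 300 pg/mL.

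On variability, Protocol 9.8 says of the Week 12 to baseline log ratio that "a SD of 0.85 was considered a reasonable estimate", with 0.8 to 0.9 as the range.

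**The concern.** If much of a patient's NT-proBNP variation is visit-to-visit noise, one baseline reading is an imprecise measure of the usual level, and a second reading explains Week 12 variance that the first cannot. The trial has already paid for that second reading.

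Precision is what is at stake. The MMRM contrasts each dose separately with placebo and with empagliflozin, whereas MCP-Mod pooled information across doses. At the planned effective size of 56 versus 112, with 0.85 as residual SD, the 95% half-width for a low dose against placebo is 1.96 × 0.85 × √(1/56 + 1/112) = 0.27 on the log scale. The planning effect of a 25% reduction is -ln(0.75) = 0.288. Early termination can be expected to make the intervals wider still.

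**Working it through.** **1. The plan's own figure.** Inputs from Protocol 9.8 and 9.4.2: effective N of 336 (112/56/56/112 for placebo, 2.5, 10 and 50 mg), SD 0.85, 25% maximum reduction, six candidate models, one-sided 2.5%. Optimal contrasts with a multivariate-t critical value of about 2.19 give mean power 74.9% and minimum 71.0%, against the stated 75% and 71%. All nine rows of Table 9-1 agree within one point. So 0.85 enters the calculation directly as the SD of the log ratio.

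**2. What 0.85 implies about noise.** If correlation is equal across visits, the within-patient SD is 0.85/√2 = 0.60. This is conditional: the SD of a 12-week change cannot separate noise from real change.

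**3. Gain under equal correlation ρ (level plus noise, no drift).** Residual variance as a share of total is 1 - ρ² given Visit 201 alone, and 1 - 2ρ²/(1 + ρ) given both values. The ratio of the two is (1 + 2ρ)/(1 + ρ)², and interval width scales with its square root.

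| ρ | variance ratio | width ratio | total log SD implied by 0.85 |
|---|---|---|---|
| 0.3 | 0.947 | 0.973 | 0.72 |
| 0.5 | 0.889 | 0.943 | 0.85 |
| 0.7 | 0.830 | 0.911 | 1.10 |
| 0.9 | 0.776 | 0.881 | 1.90 |

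The 12% end therefore needs ρ = 0.9, a total log SD of 1.90 and no truncation.

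**4. Truncation of Visit 1.** Selecting the top 50-75% of Visit 1 values (an assumed pass rate) gives width ratios of 0.974 and 0.964 at ρ = 0.5, and 0.906 and 0.895 at ρ = 0.9. Intervals are then roughly 3-10% narrower.

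**5. Drift plus noise.** Let d be the 4-week correlation of the underlying level and R the reliability of one reading. The correlations are Rd (Visit 1 with Visit 201), Rd³ (Visit 201 with Week 12) and Rd⁴ (Visit 1 with Week 12). With R from 0.80 to 0.95 and d from 0.90 to 0.98, the width ratio runs from 0.997 (R = 0.95, d = 0.90) to 0.932 (R = 0.80, d = 0.98).

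**6. Pure drift.** With R = 1, the partial covariance of Visit 1 with Week 12 given Visit 201 is d⁴ - d × d³ = 0. The width ratio is 1.000 and there is no gain.

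**7. Cross-check by simulation.** SD of change was set to 0.85, Visit 1 truncated at 300 pg/mL and between-patient SD taken as 0.8. Residual SD falls from 0.752 to 0.709 (pure noise, intervals 5.7% narrower), from 0.766 to 0.742 (half noise, 3.1%) and from 0.794 to 0.792 (no noise, 0.3%).

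**8. On the interval itself.** For 50 mg versus placebo, 112 per arm and 0.85 as residual SD, the half-width is 1.96 × 0.85 × √(2/112) = 0.223. It becomes 0.210 at ρ = 0.5, 0.196 at ρ = 0.9, and stays at 0.223 under pure drift.

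**9. Price of one uninformative covariate.** With ν = N - 7, width is multiplied by √(1 + 1/(ν - 2)) × t(0.975, ν - 1)/t(0.975, ν). Break-even partial R² is 1 - 1/width².

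| N in model | width ratio | break-even partial R² |
|---|---|---|
| 496 | 1.001 | 0.2% |
| 125 | 1.004 | 0.9% |
| 50 | 1.013 | 2.5% |
| 30 | 1.026 | 5.0% |
| 20 | 1.053 | 9.9% |

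A width ratio of 0.974, the low end in step 4, corresponds to a partial R² of 1 - 0.974² = 5.1%. At about 30 patients the price cancels it.

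**The case against.** The strongest reply is that nothing here is wrong. Adjusting for one baseline value is conventional, matches the SAP's baseline definition and was also the protocol's choice in its ANCOVA (Protocol 9.4.2). The analysis is labelled exploratory and serves an abbreviated report. This stands: the point concerns efficiency only.

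A reader might infer that the second covariate will narrow the intervals at no cost. The documents do not support either half. They give no correlation between Visit 1, Visit 201 and Week 12, and under pure drift the gain is nil. The realised sample size is not stated, and the price grows as the sample shrinks.

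A reader might also infer that the SD of 0.85 proves a single reading to be noisy. It does not, because it mixes noise with real change. Real change is plausible here: diuretic dosing is flexible (Protocol 4.1), heart-failure medication may be altered (Protocol 5.5.7), and volume status is assessed at Visit 101 and, "if hypovolemic, corrected during the run-in". That last step falls between the two pre-treatment readings, so in those patients Visit 1 may reflect a different state. Protocol 9.8 itself admits a lack of data on this SD.

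Finally, the change needs rules. Without a Visit 201 value, the SAP baseline falls back to an earlier one, normally Visit 1, so the two covariates coincide. Re-screened patients can have two Visit 1 values. A missing Visit 1 value would normally drop the patient. Giving Visit 1 a visit interaction that the baseline covariate lacks would be inconsistent. All of this stands, but can be settled in a few lines.

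**Conclusion.** The model omits a pre-randomization NT-proBNP value that the trial has by design for every patient. Adding it cannot bias the treatment comparison, since it is measured before assignment. Truncation above 300 pg/mL reduces the gain but does not invalidate the adjustment.

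The expected effect on Week 12 interval width is a reduction of 0% to about 12%, depending on which of the assumed correlation patterns is nearest the truth. The upper end holds only for high equal correlation without truncation; once truncation is allowed for, about 10% is the most that was found. The price is one or two degrees of freedom: negligible near 496 patients, but enough at 20 to widen intervals by about 5% if the covariate carries no information.

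That the mechanism is sound and free of bias is certain. The size of the gain, and whether there is one, is not. Severity is low: a worthwhile improvement to an exploratory analysis, not a fault in the SAP.

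**What to change.** Before unblinding, add to SAP 2.5.2:

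- Log-transformed Visit 1 NT-proBNP is an additional covariate in the NT-proBNP MMRM. It is handled in the same way as the baseline covariate: both as main effects, or both with a visit interaction.
- The Visit 201 value remains the baseline for the change score.
- For re-screened patients, use the Visit 1 value from the last screening.
- Where only one pre-treatment value exists, use it for both covariates, so that no patient is dropped.
- If the analysed set is very small, for example below about 50 patients, keep the single-baseline model. Apply this rule to the total number, without reference to treatment.

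The cost is a few sentences, one more variable in the model and one or two degrees of freedom. No new data are needed.

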#### **9.4.3 Handling of missing values/censoring/discontinuations**

Missing data for the primary endpoint will be imputed using a multiple imputation approach assuming that the missingness mechanism can be retrieved from observed data (missing at random (MAR)). The imputation model will include the longitudinal sequence of NT-proBNP data collected at baseline, Week 4 and Week 12 visits, stratification factors geographical region and LVEF ( $< 45\%$  versus  $\geq 45\%$ ), and other baseline covariates as appropriate.

The full detailed information about the multiple imputation algorithms will be specified in a separate statistical analysis plan.

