2.5.3 Handling of missing values/censoring/discontinuations

No imputation will be performed for missing NT-proBNP values.

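### The NT-proBNP MMRM holds the baseline slope (and the LVEF effect) equal at Weeks 4 and 12; by-visit terms would give a Week 12-specific adjustment for a modest gain at negligible cost

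*SAP*

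**What the plan says.** SAP 2.5.2 drops MCP-Mod after early termination and substitutes an MMRM: "The following analysis will be performed instead as an exploratory analysis for NT-proBNP". It still tests: "Statistical testing of hypotheses on the endpoint will be performed at the two-sided 0.05 significance level".

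After LVEF group, the fixed effects are "treatment group, visit, and treatment group-by-visit interaction will be included as fixed-effect factors". The continuous term is described as follows: "baseline log-transformed NT-proBNP will be included as a covariate, with a common unstructured covariance matrix for all treatment groups". No baseline-by-visit or LVEF-by-visit term is listed. Estimates are reported "at Week 4 and at Week 12 for each treatment group, and for the adjusted mean difference at Week 4 and at Week 12", so the model spans two post-baseline visits. This matches protocol 9.4.3, which describes "the longitudinal sequence of NT-proBNP data collected at baseline, Week 4 and Week 12 visits".

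SAP 2.5.3 adds "No imputation will be performed for missing NT-proBNP values", so missing Week 12 values are handled only through the likelihood under MAR.

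Protocol 9.4.2 specified an ANCOVA on the Week 12 log ratio alone, with log baseline as covariate and region and LVEF as factors. Those coefficients belonged to Week 12. SAP section 4 records the move to MMRM but not this side effect.

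**The concern.** The model lets treatment effects vary by visit but not the covariate effects. The unstructured covariance describes the residuals and does not free the slope.

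If NT-proBNP has a similar SD at each visit, the slope of change on baseline is about (correlation with baseline − 1). It steepens as that correlation fades, so a steeper slope at Week 12 than at Week 4 is a reasonable expectation. The likelihood then settles on a compromise that leans towards the visit with the smaller residual variance.

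Week 12 remains the primary time point. Randomisation is stratified by region and LVEF, not by NT-proBNP. The trial stopped early and the two lower-dose arms have half the allocation of the others, so chance imbalance in baseline NT-proBNP may be larger than planned. With imputation dropped, the MMRM mean model also has to carry the MAR assumption by itself.

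**Working it through.** **1. The plan's own figure.** The documents give no power or standard error for the MMRM. The nearest figure is the MCP-Mod power in SAP Table 3-1 (SD 0.85, effective N 336). Optimal contrasts for the six candidate shapes with n = 112/56/56/112 give a critical value of 2.19. Mean/minimum power is 74.8%/71.0% for a 25% reduction (stated 75%/71%) and 90.5%/88.0% for 30% (stated 90%/88%). The SD of 0.85 and the allocation can therefore be used below.

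**2. Parameter count.** As written: intercept 1 + LVEF 1 + treatment 4 + visit 1 + treatment-by-visit 4 + baseline 1 = 12. Baseline-by-visit makes 13 and LVEF-by-visit 14.

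**3. Assumptions not in the documents.** SD of baseline log NT-proBNP 0.9; SD of Week 4 change 0.75; residual correlation 0.6; slopes as listed; about 10% MAR dropout before Week 12; realised N of 48, 128 or 496 in the 1:1:2:2:2 ratio.

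**4. The slope the model applies.** With complete data, the common slope is (w4·b4 + w12·b12)/(w4 + w12), where w4 = residual variance at Week 12 − covariance, and w12 = residual variance at Week 4 − covariance. For b4 = −0.30 and b12 = −0.45:
- Residual variance at Week 4: 0.75² − 0.30² × 0.9² = 0.490
- Residual variance at Week 12: 0.85² − 0.45² × 0.9² = 0.558
- Covariance: 0.6 × √(0.490 × 0.558) = 0.314
- w4 = 0.245, w12 = 0.176
- Common slope: (0.245 × −0.30 + 0.176 × −0.45)/0.421 = −0.36

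Simulated REML fits at N = 128 gave −0.360 without dropout and −0.353 with 10% dropout. The Week 12 slope is therefore about 0.10 too shallow.

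**5. Precision.** Simulated model SE of the Week 12 difference, 50 mg vs placebo, N = 496, with 10% dropout:

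| True slopes, Week 4 / Week 12 | Common slope | Baseline-by-visit | SE change | Variance ratio |
|---|---|---|---|---|
| −0.45 / −0.45 | 0.0986 | 0.0986 | none | 1.00 |
| −0.30 / −0.45 | 0.0998 | 0.0989 | −0.9% | 1.02 |
| −0.15 / −0.45 | 0.1018 | 0.0990 | −2.8% | 1.06 |
| −0.10 / −0.60 | 0.0921 | 0.0871 | −5.4% | 1.12 |

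A separate simulation (baseline SD 0.8, 20% missing at Week 12) gave variance ratios of 1.03 to 1.05 for slopes −0.10/−0.30, 1.00 to 1.03 for −0.20/−0.35, and 0.99 to 1.00 for equal slopes.

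**6. Chance imbalance.** A one-SD imbalance between 2.5 mg and placebo is 0.9 × √(1/n₁ + 1/n₂): 0.14 at N = 496 (62 and 124) and 0.28 at N = 128 (16 and 32). For slopes −0.30/−0.45 the shift is about 0.10 × 0.14 = 0.014 log units (1.4%) at N = 496, and (0.45 − 0.353) × 0.276 = 0.027 (2.7%) at N = 128. The N = 128 shift is about 11% of that contrast's SE (0.027/0.242).

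**7. Bias.** When one dropout mechanism applied in all arms, the common-slope contrast was unbiased within simulation error, with coverage of about 94 to 96%. When MAR dropout ran in opposite directions by arm, bias was −0.013 (slopes −0.30/−0.45) to about −0.03 (−0.15/−0.45). Baseline-by-visit brought it to about zero.

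**8. Cost if the slopes are equal.** Baseline-by-visit moves the SE (50 mg vs placebo) from 0.1945 to 0.1949 at N = 128 (+0.2%) and from 0.3193 to 0.3211 at N = 48 (+0.6%). Adding LVEF-by-visit as well gives 0.1953 and 0.3230.

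**9. LVEF.** If LVEF acts only at Week 12 (0.3 log units), baseline-by-visit alone leaves the SE at 0.0996 for N = 496. Adding LVEF-by-visit gives 0.0987.

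**The case against.** The strongest reply is that this is a modelling preference in an analysis labelled exploratory. The SAP itself warns that the planned analyses may not give meaningful results after early termination. The protocol's MMRM for the other continuous endpoints (9.5.1.2) also has no baseline-by-visit term, so the SAP follows the sponsor's usual form. No document gives a slope at either visit, a Week 4 SD or a correlation with baseline. If the slopes are equal, nothing is lost. At a slope gap of 0.15 the SE gain is under 1%. The realised sample size is not stated either, so small arms are an inference.

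All of that stands, and it limits the point to a minor improvement. It does not remove it. NT-proBNP is the efficacy endpoint for which the SAP still specifies a fitted model and a 0.05 test, while the secondary endpoints in 2.6.1.2 get summaries only. The term also restores a property that the protocol's primary analysis had.

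A reader might infer that the Week 12 contrast is adjusted with a wrong slope and is therefore invalid. The documents do not support that: nothing shows that the slopes differ, and even where they do, randomisation protects the contrast on average. A reader might also infer that baseline-by-visit alone makes the Week 12 adjustment correct and is free. It is neither, because LVEF is also held constant over visits and each added term uses a parameter.

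**Conclusion.** The point holds as a minor improvement. As written, SAP 2.5.2 constrains the baseline slope and the LVEF effect to be equal at Weeks 4 and 12, and nothing elsewhere in the SAP relaxes this.

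If the slopes differ, the expected loss is roughly 0 to 5% in variance at plausible gaps; about 6% and 12% needed gaps of 0.30 and 0.50. An individual contrast may move by a few percent under chance imbalance in small arms. Bias of about 0.01 to 0.03 log units arises only under MAR dropout that differs strongly by arm. These sizes depend on the assumed slopes, visit SDs, correlation, baseline SD and N. Only the Week 12 SD of 0.85, the allocation ratio and the 10% missing-data allowance have a basis in the documents.

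**What to change.** In SAP 2.5.2, add a baseline log NT-proBNP-by-visit interaction to the MMRM, and preferably LVEF-by-visit as well, before treatment codes are opened. Note the change in SAP section 4. If the codes are already open, keep the model as written and report the extended one as a labelled sensitivity analysis.

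The cost is one parameter per term and no new data. If slopes are equal, baseline-by-visit raises the Week 12 SE by under 1% even at an assumed N of 48; both terms together raise it by about 1.2% there (0.3193 to 0.3230).
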